### Study Protocol

The focus of the project is to assess the impact of slow-wave disruption on plasticity in major depression. Following enrollment, subjects will establish a regularized bed/wake schedule based on their usual bed/wake time monitored in-home by sleep diary and actigraphy for 5 days. All subjects will then spend two nights in the sleep lab – a baseline night and an experimental slow-wave disruption night. On the experimental night, an acoustic tone will be used to decrease slow wave activity (SWA) without waking the subject. The order of nights will be determined via randomization. Between all visits, participants sleep at home on a regular sleep schedule, confirmed by sleep diaries, and actigraphic recordings.

All participants take part in 3 visits to the laboratory:

1. Visit 1: A screening and consenting visit involving informed consent, clinical assessment interviews, self-report measures, and an orientation to TMS and slow-wave disruption procedures.
2. Visit 2: A baseline night in the laboratory where participants spend the night in our sleep laboratory having their sleep monitored, followed by a morning blood draw, and assessment of mood via the clinician-administered Hamilton rating scale for depression, and battery of questionnaires including the Beck Depression Inventory II, two Visual Analogue Scales measuring positive and negative mood, respectively, and Karolinska Sleepiness Scale to assess sleepiness tasks. Additionally, participants will complete a battery of tasks including a resting EEG protocol to assess waking EEG theta power, and two learning and memory tasks, the N-Back, and Paired Associated Learning, followed by the TMS protocol, where motor evoked potentials and intracortical facilitation will be assessed.
3. Visit 3: A slow-wave disruption night where slow-wave activity will be experimentally reduced using acoustic tones administered when sleep technologists detect slow-waves from real-time EEG monitoring, followed by the same procedures as detailed in Visit 2.

Note that the order of baseline night and slow-wave disruption night is counterbalanced, with all participants undergoing both nights.

### Statistical Analysis Plan

SPECIFIC AIM 1: Compare multiple, indirect indices of synaptic strength and plasticity in patients with MDD to healthy controls, and to their relationship with SWA. Aim 1 will be achieved by testing null hypotheses that the mean values at baseline are equal between HC and MDD. Hypotheses will be tested using two-sample t-tests with adjustment for multiple outcomes addressed using the methods described above. Regression and correlation analyses will be used to evaluate the degree to which synaptic strength/plasticity variables are associated with SWA. Predictions: (Hypothesis 1.1) The MDD group will demonstrate lower values of synaptic strength (lower total theta power, lower amplitude TMS-evoked potentials) and plasticity (lower levels of serum-derived BDNF, worse performance on behavioral measures of learning and memory) compared to HC at baseline. (Hypothesis 1.2) In those with MDD there will be a positive relationship between measures of synaptic strength and plasticity (total theta power, TMS-evoked potentials, BDNF, performance on behavioral measures) and SWA in the first

NREM period that is not present in HC, such that lower values of synaptic strength and plasticity are predicted for subjects with lower SWA.

SPECIFIC AIM 2: Determine if SWA disruption alters measures of mood, and measures of synaptic strength and plasticity in a sample of individuals with MDD. Regression will be used to model if SWA is directly associated with mood, and synaptic strength/plasticity variables.

Predictions: (Hypothesis 2.1) There will be a positive relationship between SWA and negative mood scores (HAM-D, Negative VAS), such that lower SWA will be associated with lower negative mood scores. (Hypothesis 2.2) There will be a positive correlation between reductions in SWA and improvements in synaptic strength/plasticity variables (total theta power, TMS-evoked potentials, BDNF, performance on behavioral measures), such that subjects with the greatest reductions in SWA will be expected to have the largest improvements in synaptic strength/plasticity endpoints. Since the scientific hypothesis is clearly one-sided, one-sided tests of the hypotheses of zero correlation will be performed controlling the type 1 error rate for the set of 5 comparisons using Holm-Bonferroni method described above. Therefore, the first test will be conducted at a 1-sided type 1 error rate of  $\alpha=0.01$ .

SPECIFIC AIM 3: Explore if males with MDD are more sensitive to SWA and plasticity-related impairment. The MDD sample will be stratified by sex, resulting in two equal groups, males and females. The analyses described for Aims 1 and 2 will be repeated stratified by sex. Focus will be on descriptive comparisons of sex-specific effect sizes since the study is not powered for within sex comparisons. However, statistical comparisons between sex will be performed and where appropriate 95% confidence intervals for differences between sex in relevant effect sizes will be constructed in order to evaluate the likely ranges of sex-based differences. It is expected that sex differences, if any, are magnified in MDD and may be much smaller in HC. Therefore, if sex differences in HC appear relatively small, the analyses for Aim 3 will also compare male MDD and female MDD to all HC. Results from Aim 3 will be considered hypothesis generating. Predictions: (Hypothesis 3.1) MDD males will demonstrate lower SWA, and lower values of synaptic strength and plasticity (total theta power, TMS-evoked potentials, BDNF, performance on behavioral measures) compared to MDD females and HC at baseline. (Hypothesis 3.2) Males with MDD will also have larger synaptic strength and plasticity difference score values than females with MDD.

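### Aim 1 could add the randomised night order to its group comparisons: a cheap improvement to a valid t-test, not the correction of an error

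*Combined protocol and SAP*

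**What the plan says.** The Study Protocol section gives every participant an undisturbed night and a slow-wave disruption night: "The order of nights will be determined via randomization", and "Note that the order of baseline night and slow-wave disruption night is counterbalanced, with all participants undergoing both nights". The disruption night is "followed by the same procedures as detailed in Visit 2", so the blood draw, mood scales, resting EEG, two memory tasks and TMS protocol are all done twice.

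The Statistical Analysis Plan, Specific Aim 1, states the group comparison as follows: "Aim 1 will be achieved by testing null hypotheses that the mean values at baseline are equal between HC and MDD". The test is then named: "Hypotheses will be tested using two-sample t-tests with adjustment for multiple outcomes addressed using the methods described above". For the link with slow-wave activity (SWA) it says "Regression and correlation analyses will be used to evaluate the degree to which synaptic strength/plasticity variables are associated with SWA".

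No night-order term is named in any of these analyses. The text does not say whether order is counterbalanced within each diagnosis. The methods that Aim 1 cites from an earlier section are not in the available text; the citation concerns multiple outcomes only.

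**The concern.** In this design, baseline means the undisturbed night, not the first visit. With counterbalanced order, about half of the baseline values are second-session values. The memory tasks are the clearest place for a practice effect, and they are named Hypothesis 1.1 outcomes.

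Two things follow if session order moves an outcome by a similar amount in both groups. First, a plain t-test counts that movement as noise, so intervals are slightly wide. Second, if the realised share of second-session baselines differs between MDD and HC, part of the order effect enters the observed group difference. A model with group and order removes both. At stake are a little precision and protection against an unlucky allocation; the validity of Hypothesis 1.1 is not in question.

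**Working it through.** **The plan's own figure.** The only design figure is the first Holm-Bonferroni step for Aim 2: 0.05/5 = 0.01, which reproduces. Aim 1 has no stated sample size, effect size or SD, so there is nothing of its own to reproduce.

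**Assumptions (not in the documents).** 20, 30 or 40 per group; within-group, within-order SD of 1; true MDD deficit d = 0.6 or 0.8; second session raises the score by g = 0.5 SD in both groups; unadjusted two-sided 0.05. Error rates and power come from simulation, t-test against a linear model on group and order.

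**1. Order balanced within each diagnosis.** There is no bias. The t-test's residual variance rises from 1 to about 1 + (g²/4) × 2n/(2n − 2). At n = 30 this is 1 + 0.0625 × 60/58 = 1.065, so the SD is 1.032. The critical value 2.002 then acts like 2.002 × 1.032 = 2.066, giving a true error rate of about 4.3% (simulated 4.2% to 4.4%), against about 5% with the order term.

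| n per group | Power, d = 0.6: t-test → with order | Power, d = 0.8: t-test → with order |
|---|---|---|
| 20 | 43% → 46% | 67% → 69% |
| 30 | 60% → 63% | 85% → 86% |
| 40 | 74% → 76% | 93% → 94% |

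With g = 0, both models give 63% and 86% at n = 30, so here the term costs no power.

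**2. Order balanced overall but not within diagnosis.** Averaged over the randomisation, the t-test remains unbiased and its type I error is about 5% (4.8% to 5.2% at n = 20 to 40). Power at d = 0.8 goes from about 67% to 68% (n = 20) and from 84% to between 85% and 86% (n = 30) with the term.

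For the one allocation that occurs, the expected observed deficit is d − g × (share second in MDD − share second in HC):
- 60% of MDD and 40% of HC second: 0.80 − 0.5 × 0.20 = 0.70. Power at n = 30 is about 74%, against 85% with the term.
- The reverse split: 0.80 + 0.5 × 0.20 = 0.90, power about 92%.
- No true difference, either split: the t-test rejects in about 6% of trials, against 5%.

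These three lines are conditional on that split. Its chance is hypergeometric (2n participants, n baseline-first, n with MDD): a gap of 20 points or more has probability 0.343, 0.196 and 0.117 at n = 20, 30 and 40.

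**3. Cost when there is no order effect.** The term uses one degree of freedom. If order is not balanced within diagnosis, power at d = 0.8 falls on average from 86.1% to 85.4% (n = 30) and from 69.4% to 68.1% (n = 20). At a 60/40 versus 40/60 split the variance inflation is 1/(1 − 0.2²) = 1.042, and a test with 80.0% power drops to about 78%.

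**The case against.** The strongest reply is that nothing here is wrong. Randomised, counterbalanced order is the design's own control for order effects, and the t-test answers the stated null validly. A reader might infer from the 0.70-for-0.80 figure, or from the 6% rejection rate, that the planned test is biased or inflates error. The documents do not support that: both figures hold only once an uneven split has occurred, and over the randomisation neither survives. This objection stands.

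It is also fair that the gain is small, depends on an order effect that the documents do not give, and can be a small loss if that effect is absent. The percentages use unadjusted 0.05, whereas Aim 1 plans a multiplicity adjustment, so they are not the plan's operating characteristics. Applying 0.5 SD to every outcome is a convenience; practice mainly concerns the memory tasks. Finally, the earlier methods section is unavailable, so the accurate statement is that no order term is named in the available text, not that the plan is known to lack one.

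A second tempting inference is that disruption carries over into a later baseline night in MDD only, producing a false or masked deficit. The documents do not show this. Hypothesis 1.2 expects that "such that lower values of synaptic strength and plasticity are predicted for subjects with lower SWA", while Hypothesis 2.2 expects that "subjects with the greatest reductions in SWA will be expected to have the largest improvements in synaptic strength/plasticity endpoints". They point in opposite directions, and neither speaks to persistence to a later night. Participants sleep at home between visits, which may be adequate washout. An additive order term would not remove such carryover in any case, so it lends no weight to this point.

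What remains is that order is a factor the study itself assigns, and that adjusting for it in advance deals with the imbalance that actually occurs.

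**Conclusion.** The point holds as a low-cost improvement. The Aim 1 t-test is valid, with no average bias from a common order effect and type I error at or below about 5%. It is slightly less precise than it could be, and it leaves in any realised order imbalance between MDD and HC: 0.10 SD for a 0.5 SD order effect at 60/40 versus 40/60.

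The expected gain is about 1 to 3 power points at a 0.5 SD order effect. The downside is no power lost if order is balanced within diagnosis. If it is not balanced and there is no order effect, the loss is about 1 point on average and up to about 2 under that split. All of this rests on assumed group sizes, unit SD, an assumed order effect and unadjusted two-sided 0.05. The facts about the design are clear from the text; the size of the benefit is not.

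**What to change.** In Specific Aim 1, replace each two-sample t-test with a linear model on group and night order (baseline first or second), and keep the planned multiplicity adjustment. Include night order in the Hypothesis 1.2 regressions. State whether order is counterbalanced within each diagnosis, since that determines how much imbalance can arise.

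As a descriptive sensitivity analysis only, report the MDD-HC difference with its 95% CI separately by night order. Say that it is imprecise: at an assumed 30 per group, with 15 per group in each order, the half-width is t(0.975, 28) × √(2/15) = 2.048 × 0.365 = 0.75 SD. It cannot rule carryover in or out and does not replace the primary test.

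The cost is SAP wording and one degree of freedom per model, plus the small possible power loss given above. No new data are needed, because the study assigns the order and already plans to measure the outcomes.

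### Aim 1 compares the non-randomised MDD and HC groups by t-tests without covariates or described matching, so a difference in sex or age mix may be read as a diagnosis effect

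*Combined protocol and SAP*

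**What the plan says.** The Statistical Analysis Plan sets Specific Aim 1 as follows: "Compare multiple, indirect indices of synaptic strength and plasticity in patients with MDD to healthy controls". The comparison is made by "testing null hypotheses that the mean values at baseline are equal between HC and MDD", and the method is stated in one sentence, which begins: "Hypotheses will be tested using two-sample t-tests with adjustment for multiple outcomes". The only adjustment named there is for the number of outcomes. Regression does appear under Aim 1, but for another question: "Regression and correlation analyses will be used to evaluate the degree to which synaptic strength/plasticity variables are associated with SWA".

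The Study Protocol section randomises one thing only: "The order of nights will be determined via randomization". Group membership is fixed by diagnosis.

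Specific Aim 3 bears on sex in four ways.
- On composition: "The MDD sample will be stratified by sex, resulting in two equal groups, males and females". Nothing equivalent is said about HC.
- On expected effects, Hypothesis 3.1 begins: "MDD males will demonstrate lower SWA, and lower values of synaptic strength and plasticity". The comparison is with MDD females and with HC, on the same kinds of measure as Hypothesis 1.1.
- It adds that any sex differences should be larger in MDD and could be far smaller in HC.
- It repeats the Aim 1 analyses separately by sex, while calling Aim 3 hypothesis generating and conceding that power is lacking within each sex.

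**The concern.** A two-sample t-test between diagnostic groups estimates the difference in group means, whatever produces it. If HC differ from MDD in sex or age mix, and those factors are related to theta power, TMS-evoked potentials, BDNF or task performance, the Aim 1 contrast contains that difference in composition as well as any difference tied to diagnosis. Randomising night order does nothing to balance the two groups.

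Hypothesis 1.1 could then be partly supported, or partly masked, by who was recruited as a control. The multiplicity adjustment lowers the threshold for each test but leaves the bias in the estimate. Because the plan already treats sex as relevant to these outcomes, its absence from the main Aim 1 test is a choice that deserves revisiting. Leaving out a prognostic covariate can also cost precision even when the groups are balanced.

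**Working it through.** The plan gives no sample size, SD, effect size or power for Aim 1, so there is no stated figure to reproduce. The check asks how large a sex bias the plan's own description allows.

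**Inputs from the documents.** The male share in MDD is 0.5 (Aim 3). Sex differences in HC may be much smaller than in MDD, with no size given (Aim 3). The HC sex mix is not stated. Age is not mentioned.

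**Assumed inputs.** HC male share q from 0.3 to 0.7; male-female gap in HC, g, of 0, 0.2 or 0.5 within-sex SDs, males lower; 20, 40 or 80 participants per group.

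**Bias.** Take as target the MDD-HC difference standardised to equal numbers of men and women. MDD is already at that mix, so the sex gap within MDD drops out. If F is the mean in HC women, the observed HC mean is F - q·g and the standardised HC mean is F - 0.5·g. The unadjusted MDD-HC difference is therefore off by (q - 0.5)·g, of size

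bias = |q - 0.5| × g.

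With males lower, a mostly female HC group pushes the result towards Hypothesis 1.1 and a mostly male one pushes against it.

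**Effect on one test.** By normal approximation, with b the bias, the chance of rejecting when the standardised difference is zero is Φ(b/se - z) + Φ(-b/se - z), where se² = [(1 + 0.25g²) + (1 + q(1 - q)g²)]/n.

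Example: q = 0.3, g = 0.5, n = 20. Bias = 0.2 × 0.5 = 0.10 SD. se² = (1.0625 + 1.0525)/20 = 0.10575, so se = 0.325 and b/se = 0.31. With z = 1.96 the rejection rate is 0.061.

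| HC sex gap g (SD) | Bias, HC 40% or 60% male | Bias, HC 30% or 70% male | Rejection rate at two-sided 0.05, HC 30% or 70% male: n = 20 / 40 / 80 |
|---|---|---|---|
| 0 | 0 | 0 | 0.050 / 0.050 / 0.050 |
| 0.2 | 0.02 | 0.04 | 0.052 / 0.054 / 0.057 |
| 0.5 | 0.05 | 0.10 | 0.061 / 0.072 / 0.094 |

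These are rates for a single test before any multiplicity adjustment. The step-wise levels for Aim 1 are not stated. At an assumed two-sided 0.01, the last row becomes 0.014, 0.017 and 0.026. Sex bias is nil if HC are also half male, or if HC show no sex gap.

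**Age.** The corresponding bias is the difference in mean age times the slope of the outcome on age. The documents give neither, so no figure is offered.

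**The case against.** The strongest reply is that Aim 3 describes effect modification, not confounding. The sex effect is expected mainly within MDD, where the sexes are planned to be equal, and any gap in HC may be far smaller. This stands, and it limits the point. A reader might infer that the plan itself expects sex to confound Aim 1; it does not say so. A sex difference confined to MDD produces no sex bias whatever the HC mix. On the other side, the expectation about HC is hedged, and one Aim 3 comparison depends on how small the HC sex differences turn out to be, so the plan treats the matter as open.

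Second, Aim 3 repeats the Aim 1 comparison within each sex, which removes sex confounding from those comparisons. This stands as a partial safeguard. The repeat is exploratory and unpowered, does not replace the Aim 1 test, and does nothing about age.

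Third, Hypothesis 1.1 predicts lower values in MDD and makes no explicit causal claim, and no actual imbalance has been shown. That is why the point says a composition difference may be read as a diagnosis effect, not that it will be.

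A reader might also infer a seriously inflated false-positive rate. Assume 15 percentage points × 0.5 SD = 0.075 SD for sex and 5 years × 0.03 SD per year = 0.15 SD for age. The total is about 0.2 SD, and with 30 per group one two-sided 5% test would reject a true null about 12% of the time. The documents do not support that as a finding. Most of it comes from an age effect they never mention, the sample size is invented, and the planned multiplicity adjustment is ignored (about 3.5% for that test at an assumed two-sided 0.01). The sex part alone gives 5.6% to 6.3% at 20 to 40 per group.

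Finally, the SAP refers back to methods that are not in the available text. That reference concerns multiplicity, so it gives no reason to suppose covariates were specified there.

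**Conclusion.** The point holds in a limited form. The main Aim 1 test is an unadjusted comparison of two groups that were not randomised, with no matching described and no covariates specified. An Aim 1 difference cannot, by itself, be attributed to diagnosis.

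The sex contribution runs from nil to 0.10 SD, assuming HC are 30-70% male and the HC sex gap is at most 0.5 SD. It is near the lower end if the plan's own expectation for HC is right. The age contribution is unknown. The case for a change therefore rests on a better method being available at little cost, not on a demonstrated large bias. It should be made before the data are analysed, so that covariates are not chosen after results are seen.

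**What to change.** Make the main Aim 1 test a linear regression of each baseline-night outcome on diagnosis, adjusted for sex and age, and apply the same multiplicity adjustment to the diagnosis coefficients. Include whether the baseline night came first or second as a precision covariate only; night order is randomised and is not a case-mix confounder.

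Report a diagnosis-by-sex term as exploratory, because the plan expects the sex effect to differ between MDD and HC. In that case the main-effects coefficient is a weighted average of the two within-sex differences, and the interaction shows how far they diverge. Keep the unadjusted t-test as a supporting result.

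State how HC are recruited with respect to sex and age. If they are in fact matched, say so and carry the matching variables into the model; that would resolve most of the point.

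The cost is SAP wording and a few degrees of freedom. Sex is needed for Aim 3 in any case. Age is assumed to be recorded at screening, which the sponsor should confirm.

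### H1.2 and H2.2 pool men and women with MDD with no sex term, so the sex differences the plan predicts can mimic part of the H1.2 pattern and can distort H2.2 in an unknown direction

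*Combined protocol and SAP*

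**What the plan says.** All of this is in the Statistical Analysis Plan.

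- **Aim 1, method.** "Regression and correlation analyses will be used to evaluate the degree to which synaptic strength/plasticity variables are associated with SWA". No covariate is listed.
- **Aim 1, Hypothesis 1.2.** "In those with MDD there will be a positive relationship between measures of synaptic strength and plasticity". The contrast with controls reads: "NREM period that is not present in HC, such that lower values of synaptic strength and plasticity are predicted for subjects with lower SWA". The claim is made for the MDD group as a whole.
- **Aim 2, Hypothesis 2.2.** "There will be a positive correlation between reductions in SWA and improvements in synaptic strength/plasticity variables". For this, "one-sided tests of the hypotheses of zero correlation will be performed", with Holm-Bonferroni control over five comparisons and a first step at one-sided 0.01. Again no sex term is named.
- **Aim 3, Hypothesis 3.1.** "MDD males will demonstrate lower SWA, and lower values of synaptic strength and plasticity", relative to MDD females and HC at baseline.
- **Aim 3, expectation for HC.** "It is expected that sex differences, if any, are magnified in MDD and may be much smaller in HC".
- **Aim 3, Hypothesis 3.2.** "Males with MDD will also have larger synaptic strength and plasticity difference score values than females with MDD".

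Aim 3 also says that the MDD sample divides into equal numbers of men and women, and that the Aim 1 and Aim 2 analyses will be repeated within each sex. It describes that repeat as descriptive, without adequate power within sex, and exploratory in status.

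**The concern.** If two equal groups are shifted the same way on both axes of a scatter plot, the pooled points slope upward even when neither group has any slope of its own. Hypothesis 3.1 predicts exactly this arrangement for MDD: men lower on SWA and lower on plasticity. Because Aim 3 expects the shift to be much smaller in HC, the artefact would be larger in MDD than in HC, which resembles the contrast that H1.2 would count as support. This needs no imbalance of sex between MDD and HC; it arises with an even split in both.

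At stake is what a positive H1.2 result means. The study is about SWA as a driver of plasticity. A pooled correlation carried by sex would be read as an SWA-plasticity relation when it shows only that men and women differ on both.

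H2.2 has the same structure in change scores. Any sex difference in those scores enters a pooled zero-order correlation, and H2.2 is the only analysis with a stated alpha.

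**Working it through.** **The plan's own figure.** The first Holm step for five comparisons is 0.05/5 = 0.01, as stated for H2.2. The family level of 0.05 is implied, not written. No sample size, power or effect size is given, so nothing else can be reproduced.

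**Inputs.** From the SAP: equal numbers of men and women with MDD, and the directions of the predicted sex differences. Assumed, because the documents give none: 40, 60 or 80 MDD participants; sex differences d of 0.3 to 1.0 within-sex SD; HC differences half as large, with an even sex split in HC; a within-sex correlation of 0.4 for H2.2. No alpha is stated for H1.2, so one-sided 0.01 is borrowed from H2.2.

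**Formula.** With within-sex correlation w and sex differences dx and dy:

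pooled r = (w + dx·dy/4) / √[(1 + dx²/4)(1 + dy²/4)]

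**H1.2, no relation within sex (w = 0), same shift d on both variables.** This reduces to (d²/4)/(1 + d²/4). For d = 0.8: 0.16/1.16 = 0.138. For d = 1.0: 0.25/1.25 = 0.20. Rejection rates are from simulation of the Pearson test (nominal 0.01).

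| d in MDD | pooled r, MDD | pooled r, HC (d/2) | rejection, n = 40 | n = 60 | n = 80 |
|---|---|---|---|---|---|
| 0.3 | 0.022 | 0.006 | 0.014 | 0.015 | 0.016 |
| 0.5 | 0.059 | 0.015 | 0.025 | 0.029 | 0.034 |
| 0.8 | 0.138 | 0.038 | 0.070 | 0.099 | 0.137 |
| 1.0 | 0.200 | 0.059 | 0.138 | 0.211 | 0.294 |

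With sex in the model the rate was 0.009 to 0.012 in every setting run. At a two-sided 5% level (2.5% in the positive tail), the unadjusted rates at n = 40 are 3.3%, 5.6%, 13.1% and 24.1%.

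**H2.2, w = 0.4, plasticity improvement larger in men by d, one-sided 0.01.** The plan does not say how SWA reduction differs by sex, so three cases are shown. Examples: no shift, d = 0.8: 0.4/√1.16 = 0.371. Smaller in men, d = 0.8: (0.4 − 0.16)/1.16 = 0.207. Larger in men, d = 0.8: (0.4 + 0.16)/1.16 = 0.483.

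| SWA reduction in men | d | pooled r | power, n = 40 | n = 60 | n = 80 |
|---|---|---|---|---|---|
| same as women | 0.5 | 0.388 | 0.575 | 0.780 | 0.900 |
| same as women | 0.8 | 0.371 | 0.522 | 0.734 | 0.864 |
| smaller by d | 0.5 | 0.318 | 0.369 | 0.562 | 0.718 |
| smaller by d | 0.8 | 0.207 | 0.129 | 0.216 | 0.302 |
| larger by d | 0.5 | 0.435 | 0.702 | 0.891 | 0.966 |
| larger by d | 0.8 | 0.483 | 0.818 | 0.957 | 0.990 |

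The sex-adjusted test has power of about 0.59, 0.81 and 0.92 at the three sample sizes in every row. With no sex difference at all, the pooled test has about 0.61, 0.81 and 0.92.

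If both changes are larger in men and there is no relation within sex, the arithmetic is that of the H1.2 table: at n = 40 the false-positive rate is 0.025 (d = 0.5) or 0.070 (d = 0.8) instead of 0.01.

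**The case against.** **A reader might infer that sex will mask H2.2.** The documents do not support this. H3.2 concerns plasticity difference scores only, and no sentence predicts a sex difference in SWA reduction. One could argue that men with lower baseline SWA have less to lose, but the plan does not say so, and the opposite shift inflates the correlation. H3.2 also leaves the sign of the difference score undefined, so treating a larger score as a larger improvement is itself a reading. This objection stands: on what the plan predicts, the loss of power is small.

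**The H1.2 effect may be negligible.** The plan is conditional about whether sex differences exist and gives no size. At 0.3 SD the distortion hardly matters. This stands as a limit on size, not on the mechanism.

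**The marginal association may be what is wanted.** H1.2 is worded as an association. If men are lower on both variables, the pooled correlation in MDD is real, and if low SWA is why men have lower plasticity, the between-sex contrast is part of the signal. This is a fair point about the estimand, and it is why the pooled correlation should still be reported. But sex precedes SWA, so conditioning on it does not remove an SWA effect, whereas the pooled figure cannot separate SWA from anything else that differs between men and women.

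**Aim 3 already looks at this.** The stratified repeat would probably show near-zero correlations within each sex if sex were the whole explanation. It makes the problem visible, but it is exploratory and unpowered, and no rule lets it change the H1.2 or H2.2 conclusion.

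**A sex term might be intended.** The word regression allows covariates, and the SAP refers back to multiplicity methods that are not in the public text. What can be said is that the available text names no sex term.

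**Conclusion.** The concern holds for H1.2 as a consequence of the plan's own predictions: the same-direction sex differences of H3.1, smaller in HC, can give a positive pooled correlation in MDD that is weaker in HC, without any within-sex relation. It is slight at 0.3 to 0.5 SD and material near 0.8 to 1.0 SD. Sample size, shift sizes, the half-size HC shift and the H1.2 test level are all assumptions. It would go too far to conclude that a positive H1.2 result must be an artefact of sex, or that sex would reproduce a complete absence of correlation in HC.

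For H2.2 the conclusion is weaker. If SWA reduction does not differ by sex, power at n = 60 is 0.78 or 0.73 (d = 0.5 or 0.8) against 0.81 adjusted. If it does differ, the bias may go either way. Because that direction cannot be known in advance, adjustment is a sensible safeguard, but the plan gives no basis for predicting a missed effect.

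**What to change.** - **H1.2:** include sex in each regression of a plasticity variable on SWA, in MDD and in HC, and base the conclusion on the SWA coefficient given sex.
- **H2.2:** test the partial correlation of SWA reduction with improvement, given sex, at the same one-sided Holm levels. Define the sign of the difference score so that improvement is unambiguous.
- **Both:** report the pooled zero-order correlations alongside as descriptive, and keep the Aim 3 stratified results as planned.

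The cost is SAP wording and one degree of freedom. With an assumed 40 MDD participants, a within-sex correlation of 0.4 and no sex effect, power falls from about 61% to 59%. Sex is already needed for Aim 3, so no new data are required.
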